### **3.2.3 Baseline Immunogenicity Analysis Sets**

This set will include a subset of participants that will be randomly selected for assessment of baseline rSBA titers, from blood samples collected at Day 1 (pre-vaccination). At the time of the finalization of this SAP, this set is intended to include 150 participants from Group 1 and 150 participants from Group 2 (25% of the 600 targeted to be enrolled in each group). From Group 1, 150 participants have been randomly selected from the pool of randomized participants (received Step 1 and Step 2 randomizations) that received a meningitis vaccine and for whom baseline serum specimens were available. A simple random selection was performed, stratifying by vaccine arm. A similar procedure is intended for Group 2. These sets will be used for analyses of endpoints that involve meningitis immunogenicity at baseline (Day 1 visit, pre-vaccination sampling).

### **3.2.4 Durability Immunogenicity Analysis Sets**

These analysis sets will assess the longer-term durability of meningitis immunogenicity based on rSBA titers from blood samples collected at the Day 181 ( $\pm 14$  days) and Day 730 ( $\pm 45$  days) study visits. At the time of the finalization of this SAP, these sets are intended to include up to 300 participants from each of Group 1 and Group 2 (200 from the NmCV-5 arm and 100 from the MenACWY-TT arm in each group).

These sets will include participants who:

- Are included in both the Baseline Immunogenicity Analysis Set and the Per Protocol Analysis Set and had blood collected at the Day 181 ( $\pm 14$  days) or Day 730 ( $\pm 45$  days) study visits (Part A), or
- Are randomly chosen from those participants in the Per Protocol Analysis Set (not included in Part A) who had blood collected at the Day 181 ( $\pm 14$  days) or Day 730 ( $\pm 45$  days) study visits (Part B, with enough randomly selected participants to complete the sample of 300 participants per study group after determining the participants in Part A).

If future circumstances allow for assaying of all collected samples, the Durability Immunogenicity Analysis Set will include all participants in the Per Protocol Analysis Set with blood samples collected at Study Day 181 ( $\pm 14$  days) or Study Day 730 ( $\pm 45$  days).

### **3.2.5 Participants not fully randomized**

This includes participants who were enrolled, received their Group 1 or 2 assignment in Step 1 randomization but who did not proceed to Step 2 randomization. These may include participants randomized at Step 1 who no longer meet eligibility criteria, who are lost to follow-up or who remained in the study but are not randomized in Step 2 because the study reached the limit of Group 2 participants randomized and vaccinated (600). These participants will be terminated from the study and will not contribute to the evaluation of any of the study endpoints, but some of the information collected on these participants will be reported as part of study procedures.

## **3.3 Statistical Analysis Issues**

### **3.3.1 Stratification**

Unless otherwise noted, separate analyses will be conducted on Group 1 and Group 2. This is, each analysis described in this SAP will be conducted for each of the two groups, and each Table/Figure/Listing described will be produced for each of the two groups.

### **3.3.2 Non-inferiority hypothesis tests**

Endpoint specific one-sided non-inferiority hypothesis tests will be conducted under a 2.5% significance level. Each non-inferiority test will be evaluated by calculating a two-sided 95% confidence interval for the difference in proportions of participants with the specific response and comparing the lower bound of the

CI to a non-inferiority margin (otherwise noted, the margin is -0.1 and will be expressed as -10%). No p-values will be reported.

### 3.3.3 Composite Hypothesis Tests for Non-inferiority of Meningitis Vaccine Immune response

The co-primary objectives of the study are to demonstrate non-inferiority of the NmCV-5 vaccine to elicit a seroprotective response, compared to the MenACWY-TT vaccine, when administered as a single dose at either 9 months of age or 15 months of age. To achieve these co-primary objectives, the study will test the following composite hypothesis:

- Null hypothesis: the seroprotection elicited by NmCV-5 to at least one of the meningococcal serogroups A, C, W, X or Y is inferior to the response elicited by MenACWY-TT
- Alternative hypothesis: the seroprotection elicited by NmCV-5 to all five meningococcal serogroups after one dose of NmCV-5 are non-inferior to those elicited by one dose of MenACWY-TT.

Overall non-inferiority at a given vaccination age (at 9 months of age and at 15 months of age) will be declared if the criteria for non-inferiority of the vaccine seroprotection, as defined above, is achieved in all five serogroups.

### 3.3.4 Missing data

Missing data on the primary immunogenicity endpoints of interest is anticipated when conducting analyses on the mITT analysis set, with reasons including, but not limited to, loss of follow-up before Day 29, missed Day 29 visit, blood specimen not collected, or unsuccessful rSBA determination. For these analyses, a “complete case” approach will be used. If the proportion of participants with missing data exceeds 10% of the analysis set, an additional analysis using multiple imputation will be conducted. Specific details on the multiple imputation analyses are described in Section 8.2.3.

### 3.3.5 Issues in data collection

The following are data collection issues that have been identified during the conduct of the study, and for which some considerations will be done in the statistical analysis:

- A) No severity grade recorded for Erythema and Induration (Reactogenicity – Baseline and Early eCRF, and Reactogenicity – Daily Log eCRF):** Because of a programming error, missing values were allowed and not automatically queried when entered in some fields of the Reactogenicity - Daily Log eCRF. The fields affected were the severity grade for Erythema/redness and the severity grade for Induration/swelling, which in both eCRFs appear after the question “Is vaccine-related erythema or induration visible?”. The issue resulted in two different patterns of responses, both consistent with the absence of any of these events, being entered by site personnel, as described below:

	Is vaccine-related erythema or induration visible?	Erythema and redness largest diameter	Induration/swelling largest diameter	Erythema /redness	Induration/ swelling
Pattern A	No	[blank]	[blank]	None	None
Pattern B	No	[blank]	[blank]	[blank]	[blank]

For analysis purposes, response pattern B will be considered equivalent to pattern A. This is, for cases showing response pattern B, the absence of severity grade in the corresponding fields will be assumed to indicate that no event was observed, provided that the response that the response

to the question “Is vaccine-related erythema or induration visible?” is “No” and that no other related information (such as diameter) was entered. For these cases, a value of “None” for the severity field will be inputted, for analysis purposes.

**B) Surface excluded from criteria for evaluation of Erythema and Induration Severity (Reactogenicity – Baseline and Early eCRF, and Reactogenicity – Daily Log eCRF):**

Following Protocol Version 4.0, which excludes percent of the affected surface area as one of the criteria for evaluation of Erythema/redness and Swelling/induration (Table 6. Toxicity Grading Scale – Solicited Local Reactions), this variable, although collected for some participants, will not be included in analyses. Severity grades for Erythema/redness and Swelling/induration will be reported as entered in the database by site personnel, noting that effort has been made to detect, query, and reconcile cases where responses to related fields do not show the expected consistency.

**C) Feverishness symptom not collected for all participants:** Following Protocol Version 3.0, the symptom of feverishness was added as a solicited event to be collected in the Reactogenicity – Daily Log eCRF. As this addition occurred when the study was underway, the evaluation of symptom severity was not collected for all participants. Specific summaries of this symptom will report as “missing” those participants for whom it was not collected.

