7.1.2 Reactogenicity

Reactogenicity events are AEs that are common and known to occur following administration of this type of study vaccine. The following Toxicity Grading Scales will be used to grade solicited local (meningitis vaccine injection site) and systemic (subjective and quantitative) reactions:

Reactogenicity events are AEs that are common and known to occur following administration of this type of study vaccine. The following are the local and systemic solicited AE which are to be collected during the study.

Solicited local reactions: pain/tenderness, swelling/induration, and erythema/redness

Solicited systemic reactions: irritability, drowsiness/lethargy, decrease eating/anorexia, vomiting, fever, and feverish

Table 6. Toxicity Grading Scale – Solicited Local Reactions

Local (Administration Site) Reaction	Mild (Grade 1)	Moderate (Grade 2)	Severe (Grade 3)	Potentially Life-Threatening (Grade 4)
Pain/tenderness	Causes no or minimal limitation of use of limb	Causes greater than minimal limitation of use of limb	Inability to perform usual social & functional activities with the limb	Inability to perform basic self-care function OR hospitalization indicated
Swelling/induration	≤2.5 cm in diameter	>2.5 cm in diameter	Presence of ulceration OR secondary infection OR phlebitis OR sterile abscess OR drainage	Potentially life-threatening consequences (e.g., abscess, exfoliative dermatitis, necrosis involving dermis or deeper tissue)
Erythema/Redness	≤2.5 cm in diameter	>2.5cm up to 5 cm	>5 cm	Potentially life-threatening consequences (e.g., abscess, exfoliative dermatitis, necrosis involving dermis or deeper tissue)

Table 7. Subjective Solicited Systemic Reactogenicity Grading

Systemic (Subjective)	Mild (Grade 1)	Moderate (Grade 2)	Severe (Grade 3)	Potentially Life-Threatening (Grade 4)
Irritability	Causes no or minimal interference with usual social & functional activities with no intervention indicated	Causes greater than minimal interference with usual social & functional activities with intervention indicated	Causes inability to perform usual social & functional activities with intervention or hospitalization indicated	Inability to perform basic self-care function AND hospitalization indicated
Drowsiness/Lethargy				
Decrease Eating/Anorexia				

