## 2 INTRODUCTION

### 2.1 Purpose

The purpose of this Statistical Analysis Plan (SAP) is to define the statistical analyses planned for the DMID 20-0024 study. DMID 20-0024 is a Phase 3 randomized clinical trial that evaluates the safety, immunogenicity, and non-interference with concomitant routine vaccines, of a meningococcal serogroup ACYW-X Conjugate Vaccine (NmCV-5) in comparison with MenACWY-TT Conjugate Vaccine in healthy Malian infants.

[figure not shown]
This SAP is based on Version 4.0 of the Study Protocol (23 May 2023) and describes the planned statistical analyses to be conducted for reporting the results of the study. A selected set of the analyses described here may also be included in reports for Data Safety and Monitoring Board (DSMB) reports and be presented in DSMB meetings (see Section 4 of this SAP). A selected set of analyses described here will also be included in reports for WHO in support of the WHO Pre-Qualification (WHO-PQ) application for NmCV-5 (see Section 3.1 of this SAP).

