## 9 SAFETY SECONDARY OBJECTIVES

### 9.1 Solicited Local and Systemic Adverse Events (Reactogenicity)

(Secondary) Endpoint: All solicited AEs reported during a 7-day follow-up period after meningococcal vaccination.

Per protocol, solicited injection site (local) and systemic reactogenicity adverse events are intended to be collected from time of study meningococcal vaccination through 7 days after each vaccination. Reactogenicity is intended to be first assessed about 30 minutes post-vaccination, then routinely assessed during the first four days post-vaccination and again on Day 8 Visit (Study Visit 2, scheduled at Day 8 with + 3-day window). For instances where there is reactogenicity of grade 2 or higher at the fourth day post-vaccination (Day 5), then daily assessments are intended to continue, until resolution or the severity of the reactogenicity is grade 1 (Mild). Severity grade for solicited AEs is recorded as none, mild, moderate, Severe and Potentially Life Threatening. Systemic AEs include Body temperature, Irritability, Drowsiness/Lethargy, Decrease Eating/Anorexia, Vomiting and Feverishness. Local AEs include erythema/redness (severity and largest diameter in cm), induration/swelling (severity grade and largest diameter in cm), and pain and/or tenderness.

For this safety endpoint, all reactogenicity symptoms reported after receipt of meningitis vaccination at Study Day 1 to Day 7 (including early assessment post-vaccination) will be included, as well as symptoms reported for Study Day 8, as long as the Day 8 assessment visit occurred within the specified visit window. Symptoms will be reported according to the Study Day for which they were reported in the Reactogenicity - Baseline and Early and Reactogenicity - Daily Log eCRFs.

Analysis Set: mITT Analysis Set

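### Erythema and swelling grades are reported as entered although a grading criterion was dropped mid-trial, and the SAP does not say whether earlier grades were aligned to Table 6

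*SAP*

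**What the plan says.** SAP 3.3.5 B describes a mid-trial change. It refers to Protocol Version 4.0 as the version "which excludes percent of the affected surface area as one of the criteria for evaluation of Erythema/redness and Swelling/induration". Of the surface-area variable it says: "this variable, although collected for some participants, will not be included in analyses". The grades themselves are kept: "Severity grades for Erythema/redness and Swelling/induration will be reported as entered in the database by site personnel". The same sentence adds that "effort has been made to detect, query, and reconcile cases where responses to related fields do not show the expected consistency".

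The current scale is Protocol 7.1.2, Table 6. Its lower grades rest on size, for example "Swelling/induration ≤2.5 cm in diameter" for swelling Grade 1 and ">2.5cm up to 5 cm" for erythema Grade 2.

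SAP 9.1 confirms that grade and diameter are both recorded: "Local AEs include erythema/redness (severity and largest diameter in cm), induration/swelling (severity grade and largest diameter in cm". It tabulates maximum severity by symptom and arm, summarises events by day and severity, and gives separate summary statistics for largest diameter.

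**The concern.** Leaving a grading input out of the tables does not undo its effect on a grade that has already been assigned. If an infant was graded while surface area still counted, the stored grade may reflect it. The SAP does not say that such grades were reassigned to Table 6, how many there are, or that results will be shown by protocol version.

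Item C of the same section is more open about another mid-trial change. Infants for whom feverishness was not collected will be shown as missing. Item B gives the reader no comparable way to see who is affected.

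At stake is the meaning of the severity rows for two local reactions in a secondary safety endpoint. The same visible reaction could sit in different rows depending on when it was graded.

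**Working it through.** The plan states no figure on this point, so there is nothing to reproduce. The check has three steps.

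**1. Does the text establish one scale?** Three statements from SAP 3.3.5 B and 9.1, side by side:
- A criterion was removed in Version 4.0 after data on it had been collected for some infants.
- Grades are analysed as the site entered them.
- Inconsistent related fields were queried and reconciled.

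Only the third could bring grades onto one scale, and it does not say what the fields had to be consistent with. A grade that agreed with the criteria in force when it was entered need not have raised a query. So the text neither establishes one scale nor proves two.

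**2. How far can recorded diameter supply a common scale?** From Table 6:

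| Reaction | Grade 1 | Grade 2 | Grade 3 | Grade 4 |
|---|---|---|---|---|
| Erythema | diameter | diameter | diameter | clinical features |
| Swelling | diameter | diameter | clinical features | clinical features |

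Diameter settles 3 of 4 erythema grades and 2 of 4 swelling grades. The SAP describes no separate field for the clinical features, so the site grade has to stand for the other three cells.

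**3. How many infants could be involved?** The inputs are the planned arm sizes of 400 and 200 per age group (Protocol 2.1, Table 5) and the local reaction rates of 1.3%, 3.0% and 0.7% in the earlier trial in Malian children (Protocol 1.1.2). Expected count = n × rate.
- NmCV-5: 400 × 0.007 = 2.8, up to 400 × 0.030 = 12.0.
- MenACWY-TT: 200 × 0.007 = 1.4, up to 200 × 0.030 = 6.0.

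These are infants with any local reaction. Pain is included, so the counts for erythema or swelling would be no higher at the same rates.

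The share graded under the earlier criteria is not given. Assuming 25% to 75%:
- NmCV-5: 2.8 × 0.25 = 0.7, up to 12.0 × 0.75 = 9.0.
- MenACWY-TT: 1.4 × 0.25 = 0.35, up to 6.0 × 0.75 = 4.5.

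These count infants who could carry an earlier-criteria grade, not grades that would change. Each infant who did change rows would move a percentage by 1/400 = 0.25 points or 1/200 = 0.5 points.

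The earlier trial reported only mild solicited reactions apart from one moderate fever, so no local reaction there was above mild. Taking 0 of 375 (all randomised children, an assumed denominator), the exact upper limit is 1 − 0.025^(1/375) = 0.98%. That is about 3.9 of 400 and 2.0 of 200 with a local reaction of Grade 2 or higher.

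**The case against.** The strongest reply is that the problem may already be solved. With surface area set aside, the fields shown beside each grade in SAP 3.3.5 A are the visibility question and the diameter. Reconciling grades against those could well have aligned them with Table 6. The superseded scale is not in the documents, so nobody can show that even one grade would change. Safety is descriptive, without tests (Protocol 9.2). Largest diameter does not depend on the grading scale and is already summarised. The SAP also discloses its choice openly.

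Most of this stands, and it limits the size of the point. It does not close the gap, because the SAP does not say which scale the reconciliation used. If every grade was aligned to Version 4.0, one sentence saying so would answer the main question.

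A reader might also infer that recorded diameter would replace the site grade altogether. Table 6 does not allow that, since swelling Grade 3 and all Grade 4 reactions rest on clinical features.

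**Conclusion.** The gap is real but minor. The SAP leaves open whether grades entered before Version 4.0 follow Table 6, so the severity tables for erythema and swelling may mix two sets of criteria. The number of affected grades cannot be computed and is probably small. That judgement assumes local reactions about as rare and as mild as in the earlier Malian trial.

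The comparison between vaccines is not in doubt. Step 2 allocation is 2:1 in blocks within each age group, and the evaluators are blinded, so any mixture should fall about evenly on the two arms.

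Three stronger readings are tempting, and the documents support none of them:
- **That two scales are in fact pooled.** This is an inference. The earlier scale is not shown, and some or all grades may have been reconciled.
- **That severity is biased between the 9-month and 15-month groups.** Vaccination dates are not given, so where the change of 23 May 2023 falls in each group is unknown. The groups are analysed and reported separately, and the only planned comparison between ages is of immune response.
- **That SAP 3.3.5 A shows these grades to be unreliable.** It describes blank fields in records consistent with no reaction, not wrong grades for actual reactions.

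**What to change.** In SAP 3.3.5 B, state whether grades entered before Version 4.0 were reconciled to Table 6, and for how many infants in each group.

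In SAP 9.1, add a severity table for all infants that derives erythema Grades 1 to 3 and the swelling Grade 1/2 split from recorded largest diameter, using the existing Table 6 cut-offs. Keep the site-entered grade for swelling Grade 3, for all Grade 4 reactions, and where diameter is missing for a visible reaction. Flag those cases. List every case where the derived and site grades differ.

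The diameters are already in the database, so no new data are needed. The cost is a small amount of programming, and the table remains partly dependent on site grades where diameter does not decide.

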## 4 INTERIM ANALYSIS AND SAFETY MONITORING COMMITTEE

No interim statistical analyses will be conducted, understanding by this the sequential testing of a statistical hypothesis for which adjustment of type I error probability is required.

### 4.1 Data and Safety Monitoring Board Reports

Safety oversight will be conducted by a DSMB. The DSMB will review SAEs on a regular basis and on an ad hoc basis during the trial. The DMID Medical Monitor and the Independent Safety Monitor (as deemed necessary) will be responsible for reviewing SAEs in real time. If any of the halting rules listed in Section 7.6 of the protocol are met, cumulative safety data from all enrolled subjects will be summarized for DSMB review.

In addition to any unscheduled DSMB reviews resulting from halting rules being met, the DSMB will review cumulative AE data as follows:

- A safety review will be conducted after all participants randomly assigned to receive the meningococcal vaccine at 9 months of age have completed Day 29 visit.
- A safety review will be conducted after all participants randomly assigned to receive the meningococcal vaccine at 15 months of age have completed Day 29 visit.
- As per DSMB request, a review of the available study data from the 9 months of age group subjects will be conducted prior to initiating dosing of subjects randomized to receive meningococcal vaccine at 15 months of age subjects.

The DSMB will have access to closed study reports with information presented by vaccine arm, without masking. This is due to simple masking not being possible under unbalanced randomization (2:1) and other masking strategies deemed cumbersome.

Procedures for DSMB reviews/meetings are defined in the corresponding DSMB charter.

## 5 GENERAL ANALYSIS METHODS

The following descriptive statistics will be used to summarize continuous outcomes: number of non-missing values, mean and standard deviation, median, interquartile range, and range (minimum and maximum). Descriptive statistics for categorical endpoints may include number of non-missing values, frequencies, relative frequencies, and percentages.

Additionally, descriptive summaries of immunogenicity data may include Geometric Means (GM), proportion of participants showing levels above a certain pre-defined cutoff or proportion of participants achieving a pre-specified increase from baseline.

For selected binary endpoints, 95% exact binomial Confidence Intervals (CI), calculated using the Clopper-Pearson method, may be presented. For GM, the corresponding 95% CIs will be based on the log-transformed endpoint and calculated based on a t-distribution with degrees of freedom equal to n-1 (where n denotes the number of observations).

To identify the different randomization arms/groups, the following naming conventions will be used in this SAP and for reporting and displaying of the data analyses.

- “Participants assigned to receive vaccine at 9 months of age” or “Group 1” will be used to describe those screened and enrolled participants who at Step 1 randomization are assigned to receive their meningitis vaccine immediately, noting that the eligibility age range is 9 to 11 months of age.
- “Participants assigned to receive vaccine at 15 months of age” or “Group 2” will be used to describe those screened and enrolled participants who at Step 1 randomization are assigned to receive their meningitis vaccine about 6 months after Step 1 randomization, noting that the eligibility age range is 15 to 17 months of age.
- Within the two groups described above, the term “by vaccination arm” or simply “by arm” will refer to the groups resulting from random vaccine assignment performed at Step 2 randomization (NmCV-5 vs MenACWY-TT).

All summaries and statistical analyses will be produced using SAS statistical software, Version 9.4 of the SAS System for Linux, Copyright © 2013 SAS Institute Inc [3] (SAS and all other SAS Institute Inc., product or service names are registered trademarks or trademarks of SAS Institute Inc., Cary, NC, USA). The R statistical software [4] can also be used to produce (or replicate) selected figures.

